5.2 SECONDARY ENDPOINT(S)

5.2.1 Key secondary endpoint(s)

No key secondary endpoints are defined in this study.

5.2.2 Secondary endpoint(s)

Phase I

- Number of subjects with objective response combining
 - Complete remission (CR)
 - CR with incomplete blood count recovery (CRI)

- Time frame: From start of treatment until the earliest of progression, death or end of trial (approximately up to 30 months).

6. GENERAL ANALYSIS DEFINITIONS

6.1 TREATMENT(S)

Phase I

In the Phase I Part, treatments are not randomized (open-label, dose escalation). Different dose levels of the investigational medicinal product (BI 836858) can arise while combined with fixed dose of decitabine at 20 mg/m² per day. The data will be presented for all dose cohorts separately, in particular, subjects will be analysed by the dose cohort initially assigned in the first treatment course.

Table 6.1:1 Definition of analysing treatment periods

Analysing treatment period	Start date (including)	Stop date (excluding)
Screening	Date of informed consent	Date of first administration of trial medication
MTD evaluation period	Date of first administration of trial medication	First of start of the second treatment cycle or the end of the 30-day residual effect period
On-treatment	Date of first administration of trial medication	Start date of 'Follow-up'
Follow-up	Date of end of REP +1	Start date of 'Post-study'
Post-study	Last date subject status obtained / last date subject known to be alive + 1 (if subject is lost to follow-up) / date of refusal + 1 day / the date subject died + 1	During the trial: open / empty; after database lock (DBL): DBL + 1 day

Data recorded between the first administration of trial medication until up to 30 days (Residual effect period; REP) after the last administration of trial medication will be considered as on-treatment.

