Administration of BI 836858 ^{17,18} (for details on BI 836858 administration refer to Table 4.1.3.1: 2 and 4.1.3.2: 1)						x***	x***		x	x			x			x	x	x		
Eligibility check for (further) drug administration of BI 836858						x	x		x	x			x	x		x	x	x		

Trial Protocol

Proprietary confidential information © 2019 Boehringer Ingelheim International GmbH or one or more of its affiliated companies

*) The planned duration of a treatment cycle is 28 days. Day 1 of each cycle is defined as the day when the first dose of decitabine in that cycle is administered. The start of the next cycle must not be earlier than Day 29 of the previous cycle. There will be a maximum of 4 administrations of BI 836858 in one treatment cycle (with the exception of treatment Cycle 1, where there is a maximum of 3 administrations of BI 836858). All assessments should be performed prior to dose administration on dosing days, unless otherwise specified.

**) Days are calculated as calendar days. Please refer to [Section 6.2](#) for details on time windows for visits and individual study procedures or assessments.

***) In case treatment with BI 836858 cannot be started on Day 8 of Cycle 1 (due to documented medical or administrative reasons), the first dose of BI 836858 may be administered on Day 9 of Cycle 1 (at the latest). All procedures described in this [Flow Chart](#) for Day 8, Day 9 and Day 10 (especially blood sampling for PK and biomarkers as per [Table 1](#) and [Table 3](#)) should be shifted accordingly.

****) Day 29 (Visit 4) can be the same day as Day 1 (Visit 1) of the next treatment cycle if the patient is eligible to receive further treatment without delay. In that case Day 29 becomes Day 1 of next cycle, and all procedures and assessments as indicated for EOC and Day 1 of the next cycle have to be performed.

In case a patient does not continue immediately with the next cycle for any reason (and not moving to EoT), additional visits are recommended to be performed on a weekly basis, at investigator's discretion, in the period until the next cycle starts. These additional (unscheduled) visits should be documented in eCRF.

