4.1.4.3 BI 836858 dose reduction and dose escalation criteria

Administration of the trial drugs (i.e. both, decitabine and BI 836858 for patients receiving the combination treatment) has to be stopped temporarily in case of a DLT (see [Section 5.3.1](#)). Patients may continue therapy only after recovery from the DLT to a CTCAE level which allows further therapy based on Investigator assessment and only with a reduced dose of BI 836858. No dose levels for the new dose of BI 836858 have been pre-defined; any new dose outside of the currently tested dose level/cohort must be finally agreed on between the Sponsor and the Investigator. The reduced dose will be valid for all following treatment cycles in the individual patient. A reduction of the dose will be allowed only once for an individual patient during the whole trial. In case a patient experiences a second episode of DLT with the reduced BI 836858 dose, the treatment with BI 836858 has to be permanently discontinued. Likewise, treatment with BI 836858 has to be discontinued in case the DLT is not reversible. In Phase I such patients will need to be withdrawn from study treatment, perform EOT and EoR visits and followed-up as per protocol. Patients in Arm 1 of Phase II however may continue on decitabine monotherapy at the discretion of the investigator.

Intra-patient dose escalation

Intra-patient dose escalation may be considered in agreement between the Investigator and Sponsor for selected patients. It is restricted to patients who have received at least 4 administrations of BI 836858 and tolerated the treatment well up to the time of dose escalation. Intra-patient dose escalation can only be performed at a time when the next higher dose cohort has been reviewed and considered safe by the SMC. The dose escalation step is limited to the dose which has been administered to the next higher cohort. In addition, after the first dose at the higher dose level, patients have to be monitored for at least 24 h after the end of the infusion, including safety laboratory 24 h after the first administration of the escalated dose of BI 836858.

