7.3.1 Primary endpoint analyses

Phase I:

In order to estimate the MTD, the occurrence of a DLT in the first treatment cycle will be assessed on an individual patient level. However, for those patients who receive more than one cycle of the combination treatment, all AEs that constitute a DLT will be considered for re-estimation of the MTD based on the BLRM. To obtain this, the model will be re-run including the DLT information from all cycles. Based on both MTD estimates, the recommended dose for the extension cohort (and the Phase II part) will be determined. The MTD will be determined using the BLRM as described in Section 7.1.1. The number of DLTs at each dose level will be presented (all cycles and first cycle separately).

Phase II:

Objective response (CR+CRi) will be analyzed descriptively in terms of objective response rate (ORR), defined as the proportion of patients with complete response (CR) or complete response with incomplete blood count recovery (CRi).

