7.4 PRIMARY ENDPOINT(S)

Phase I

The primary endpoints are the MTD and the occurrence of DLT. The MTD is determined from the number of non-replaced subjects with DLT during the MTD evaluation period.

The MTD evaluation period is defined as the time from the first administration of study treatment to the start of the second treatment cycle or the end of the 30-day residual effect period after the last drug administration, whichever comes first. Subjects who were replaced during the MTD evaluation period are not considered for MTD determination. Those subjects who have completed the MTD evaluation period without having been replaced are referred to as subjects evaluable for MTD.

An overall summary of subjects with DLT(s) which occurred during the MTD evaluation period and the on-treatment period will be provided for each dose cohort.

Subjects who were treated but replaced are not considered for the MTD determination.

However, all information, including adverse events qualifying for a DLT from later times, will be considered in the final determination of the recommended Phase II dose (RP2D).

In order to describe the occurred dose escalation steps, a listing of all treated subjects will be provided. This will include the initial dose of the investigational medicinal product, subject number, treatment start date, DLT in MTD evaluation period [y/n], Evaluable for MTD [y/n] and will be sorted by treatment start date.

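### By-dose AE tables and the on-treatment DLT summary count events after a within-patient dose change under the initial dose; a companion summary by dose at onset is needed

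*SAP*

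**What the plan says.** **Attribution.** SAP 6.1 presents Phase I data by dose cohort and adds that "subjects will be analysed by the dose cohort initially assigned in the first treatment course". Its on-treatment period runs from the first administration to 30 days after the last, whatever dose is given in between.

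**Tables that use it.** SAP 7.8.1 refers back to Section 6.1 for the treatment definition, tabulates AEs by treatment and summarises the user-defined AE categories by dose cohort. For DLTs, SAP 7.4 plans this: "An overall summary of subjects with DLT(s) which occurred during the MTD evaluation period and the on-treatment period will be provided for each dose cohort".

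**Dose changes.** Protocol 4.1.4.3 states: "Intra-patient dose escalation may be considered in agreement between the Investigator and Sponsor for selected patients". On eligibility it says: "It is restricted to patients who have received at least 4 administrations of BI 836858". The patient must have tolerated treatment well, and the safety committee must already have reviewed the next higher cohort and considered it safe. On size: "The dose escalation step is limited to the dose which has been administered to the next higher cohort". The same section allows one dose reduction after a DLT, which then holds for all later cycles.

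**Later DLTs.** Protocol 7.3.1 says that for patients treated beyond Cycle 1 "the model will be re-run including the DLT information from all cycles", and it uses both MTD estimates to choose the dose. SAP 7.4 says later DLTs are considered for the recommended Phase II dose.

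**Mitigation.** SAP 7.8.1 adds a listing of the treatment the patient was actually receiving when each AE began.

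**The concern.** A by-dose safety table is read as a statement about that dose. Under the SAP's rule, an event that begins after escalation goes into the row of a dose the patient no longer receives. The row for the dose actually given loses both the event and the patient who was exposed. Apparent toxicity moves down the dose scale, and the higher dose looks safer than it was. After a reduction the misplacement runs the other way: later events stay with the higher initial dose.

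The SAP expects doses to change. Its important protocol deviations (Table 6.2:1) include unjustified intra-patient escalation, which implies that justified escalation can occur. Its rule for collapsing AE occurrences into episodes asks whether treatment changed between onsets. Yet its only output by actual dose is a listing, which has no denominator and leaves the tables as they are. With 16 patients in the dose escalation part (protocol synopsis), one misplaced event is visible in a row.

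**Working it through.** **1. When can a dose change occur?** Escalation needs at least four administrations. The protocol flow chart footnote describes Cycle 1 as the cycle "where there is a maximum of 3 administrations of BI 836858". An escalated infusion therefore falls in Cycle 2 or later, after the MTD evaluation period of SAP 5.1 has ended. Counting the split first dose (Days 8 and 9) as two would not alter this: the fourth infusion would be that of Day 23, and the next belongs to Cycle 2. A reduction follows a DLT, so that patient already counts as having a DLT at the initial dose. First-cycle DLT counts by patient are unchanged either way.

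**2. Crude counts.** Assumptions, since the documents give no data: cohorts of three at 20 and 40 mg; one patient who started at 20 mg is escalated to 40 mg and has a late DLT there; no other DLTs.
- Initial cohort: 1/3 at 20 mg, 0/3 at 40 mg.
- Dose at onset: 0/3 at 20 mg and 1/4 at 40 mg if the patient counts at both doses, or 0/2 and 1/4 if counted at 40 mg only.

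**3. Reproducing the protocol's model.** I used the model of protocol 7.1.1 with the priors of Table 7.1.1:3, and 2,000,000 prior draws weighted by the binomial likelihood. At decitabine 20 mg/m², its reference dose:
- logit(π1) = log(α1) + β1·log(d/160) and logit(π2) = log(α2)
- π0 = π1 + π2 − π1·π2
- odds(π) = odds(π0)·exp(η·d/160), with η ~ N(0, 0.993²)
- P(OD) = P(π ≥ 0.33 given the data)

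| Check | Protocol | Recomputed |
|---|---|---|
| Prior P(OD) at 20 / 40 / 80 / 160 mg | 0.133 / 0.186 / 0.312 / 0.537 | 0.135 / 0.190 / 0.313 / 0.538 |
| Scenario 5 (0/3 at 20, 1/3 at 40): P(OD) at 40 / 80 mg | 0.103 / 0.244 | 0.103 / 0.260 |
| Scenario 9 (1/3 at 20, 0/3 at 40): P(OD) at 40 / 80 mg | 0.086 / 0.201 | 0.085 / 0.207 |

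The largest gap is 0.260 − 0.244 = 0.016. That gap straddles the 25% limit, so I rest nothing on a threshold crossing. The comparisons below all use the same draws.

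**4. If the two codings were used in the all-cycle re-run.** Escalation from 20 to 40 mg:

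| Coding | Data (20; 40 mg) | P(OD) 20 mg | P(OD) 40 mg | P(OD) 80 mg |
|---|---|---|---|---|
| Initial cohort | 1/3; 0/3 | 0.047 | 0.085 | 0.207 |
| Onset, counted at both doses | 0/3; 1/4 | 0.034 | 0.075 | 0.221 |
| Onset, counted at 40 mg only | 0/2; 1/4 | 0.047 | 0.094 | 0.243 |

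The difference at 80 mg is 0.221 − 0.207 = 0.014 to 0.243 − 0.207 = 0.036.

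Escalation from 40 to 80 mg, with 0/3 at 20 mg:

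| Coding | Data (40; 80 mg) | P(OD) 80 mg | P(OD) 160 mg |
|---|---|---|---|
| Initial cohort | 1/3; 0/3 | 0.095 | 0.360 |
| Onset, counted at both doses | 0/3; 1/4 | 0.106 | 0.430 |
| Onset, counted at 80 mg only | 0/2; 1/4 | 0.122 | 0.445 |

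The difference at 160 mg is 0.430 − 0.360 = 0.070 to 0.445 − 0.360 = 0.085.

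In both examples initial-cohort coding gives the lower overdose probability at the dose above. No dose changes sides of the 25% limit: the 80 mg values are all below it and the 160 mg values all above.

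**The case against.** **Small stakes.** No document says that any patient changed dose, the first-cycle MTD is untouched, and development has stopped with Phase II cancelled (SAP 3 and 4). All of this stands. The consequence is for reporting and for any all-cycle re-run.

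**The listing is enough.** In a trial of this size an escalated patient can be checked individually. That helps a careful reader, but the tables and the DLT summary remain as defined.

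**Initial-cohort grouping is sound.** It keeps each patient in one row. Grouping by actual dose has its own bias, because only patients who tolerated treatment well may be escalated. This also stands, and it is why the initial-cohort tables should be supplemented and not replaced.

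**A stronger reading a reader might infer: late DLTs enter the model at the lower dose.** The documents do not say this. Protocol 7.1.1 counts DLTs at a dose combination without mentioning the initial cohort, and the visible SAP does not describe the all-cycle re-run. Parts of the SAP are blacked out, so the most one can say is that the dose is not specified in the text available.

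**A larger effect a reader might infer from scenarios 1.1 and 2.1 of Table 10.2:1.** There P(overdose) at 20 mg rises from 0.040 to 0.153 when 0/3 becomes 1/3. Both scenarios contain 20 mg data only, whereas escalation requires the higher cohort to have been reviewed already. With 0/3 at 40 mg included, the value at 20 mg is 0.047 under initial-cohort coding and 0.034 to 0.047 by dose at onset.

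**Conclusion.** The point holds for the by-dose AE and user-defined category tables and for the on-treatment DLT summary. As written, these attribute events on a changed dose to the initial dose, and the listing does not correct them. The error can run in either direction: escalation flatters the higher dose, and reduction flatters the lower one.

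It does not reach the Cycle 1 DLT count or the first-cycle MTD estimate. It is zero if no patient changed dose.

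In crude counts, a single event can move a row from 0/3 to 1/3. In the model the shift from one event is modest: about 0.21 instead of 0.22 to 0.24 at 80 mg in the first example, and 0.36 instead of 0.43 to 0.445 at 160 mg in the second. The model figures also assume that the re-run would follow the SAP 6.1 coding, which the documents leave open. All of these figures rest on assumed cohorts of three with one escalated patient and one late DLT.

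**What to change.** - **SAP 6.1:** keep the tables by initial cohort, and Cycle 1 outputs by assigned dose.
- **SAP 7.4 and 7.8.1:** add AE and on-treatment DLT summaries by actual BI 836858 dose at onset, with the patients exposed at that dose as denominator. Protocol 4.1.4.3 predefines no reduced dose levels, so allow a row for doses that match no cohort.
- **Footnote:** escalated patients are selected for good tolerability, so rows by dose at onset are not a clean dose comparison.
- **All-cycle model re-run:** state in SAP 7.4 that a late DLT is entered at the dose received at onset, with patients counted at each dose they received.

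**Cost.** The dose at AE onset is already needed for the planned listing. What remains is SAP wording, exposure counts by actual dose and a few table rows. Patients who change dose will appear in more than one row of the supplementary table, which a footnote should say.

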6.2 IMPORTANT PROTOCOL DEVIATIONS

Even though no per protocol population is defined, subjects with potentially important protocol deviations (iPD) will be identified and documented. Potentially important protocol deviations are defined in [Table 6.2:1](#). The final list of iPDs will be confirmed at the last report planning meeting (RPM) before the database lock at the time of the CTR.

If any manual iPDs are identified, they are to be summarized into categories and will be captured in the MQRM/RPM minutes via an accompanying Excel spreadsheet [\(3\)](#).

Table 6.2:1 Important protocol deviations

Category/ Code		Description	Comment/Example	Excluded from
A		Inclusion/Exclusion Criteria		
A1		Criteria related to safety		
A1.1		Patient has condition that may cause additional risk from study medication	EX 7, EX 12, EX 19	None
A1.2		Patient has laboratory assessments that may cause additional risk.	EX 8-11	None
A1.3		Patient is unable to comply with the protocol	EX 13, EX 20	None
A2		Criteria related to efficacy		
A2.1		Patient does not have trial diagnosis or is not part of the target population	IN 1-4, EX 1, EX 2	None
B		Legal criteria		
B1		Informed consent not available/not done	IN 5	All
B2		Informed consent after visit 1	IN 5	None
B3		Men or women who are sexually active and not using adequate contraception.	EX 16, EX 17	None
B4		Pregnant or nursing female patient	EX 15	None
B5		Patient's age < 18	IN 1	None
C		Administration of trial medication not in accordance with the protocol		
C1		Administration of trial medication not in accordance with the protocol	As marked in the eCRF, review and decision at medical and quality review meetings (MQRM) / report planning meetings (RPM)	None

[figure not shown]
Table 6.2:1 Important protocol deviations (cont.)

Category/ Code	Description	Comment/Example	Excluded from	
	C2	Continuation of treatment although criteria for re-treatment are not met	Create listing, decision at medical and quality review meetings (MQRM) / report planning meetings (RPM)	None
	C3	Unjustified intra-patient dose-escalation	Create listing, decision at MQRM / RPM	None
	C4	Withdrawal of patient not performed according to CTP	Create listing, decision at MQRM / RPM	None
	C5	Discontinuation of decitabine not performed according to CTP	Create listing, decision at MQRM / RPM	None
	C6	Discontinuation of BI 836858 not performed according to CTP	Create listing, decision at MQRM / RPM	None
D		Restrictions		
	D1	Additional experimental anti-cancer, chemo-, immuno-, hormone - or radiotherapy during the study or too shortly before the study.	Create listing, decision at MQRM / RPM (and EX 6)	None
E		Missing data		
	E1	Baseline bone marrow assessment not within 14 days prior to first treatment	Create listing, decision at MQRM / RPM	None
	E2	Missing disease assessment at a time point where disease assessment was required	Create listing, decision at MQRM / RPM	None

6.3 SUBJECT SETS ANALYSED

Where applicable, the following subject sets will be defined for the Phase I and Phase II part separately.

- Screened set (SS): This subject set includes all subjects who have signed the informed consent. The SS will be used for subject disposition tables.
- Treated set (TS): This subject set includes all subjects who were documented to have received at least one dose of trial medication.
- MTD evaluable set: This subject set includes all subjects who were entered, treated and completed first cycle of planned treatment or subjects received at least 2 doses of BI 836858 due to BI 836858-related toxicity but not replaced.

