Cohort 3	[REDACTED] ^{c)}	20 mg/m ²
Cohort 4	[REDACTED] ^{c)}	20 mg/m ²
Cohort 5 ^{d)}	[REDACTED] ^{c)}	20 mg/m ²

- a) BI 836858 will be administered in weekly intervals, e.g. on Days 1, 8, 15 and 22 of 28-day treatment cycles with the exception of Cycle 1, where BI 836858 will be administered for the first time on Day 8 (or Day 9 at the latest), followed by further weekly administrations, e.g. on Days 16 and 23 of the first cycle. In case WBC on Day 8 (or Day 9) of Cycle 1 is $\geq 10 \times 10^3/\mu\text{L}$, treatment with BI 836858 will not be initiated and the patient will be withdrawn from the trial treatment and replaced within the corresponding cohort (i.e. patients may be treated with decitabine monotherapy according to local standard of care and followed up as per protocol).
- b) For patients who achieve CR during any of Cycles 1 through 4, the weekly administration of BI 836858 should continue for one additional cycle and should then be reduced to monthly administration (maintenance treatment, starting on Day 1 of the next cycle).
After completion of Cycle 6 and only for patients with CR or CRi the weekly administration of BI 836858 will be reduced to monthly administration, starting on Day 1 of Cycle 7 (maintenance treatment).
- c) Dose levels above 40 mg will only be explored after safety data from monotherapy studies with BI 836858 have become available and if data from PK and pharmacodynamics analysis support further dose escalation.
- d) Further cohorts with intermediate or lower dose levels may be explored, depending on the number of DLTs observed in the trial, and dose levels higher than 320 mg of BI 836858 may be investigated if recommended by SMC and agreed upon between Investigators and Sponsor. Additional Phase I Dose Escalation cohorts may also be opened if deemed necessary by the Sponsor and the SMC following the Phase I Extension cohorts of the trial.

A time interval of at least 7 days must have elapsed between the 1st administration of BI 836858 and initiation of treatment with decitabine to the next patient in treatment Cohort 1.

A time interval of at least 3 days must have elapsed between the 1st administration of BI 836858 and initiation of treatment with decitabine to the next patient in treatment Cohort 2 or higher (see [Table 4.1.3.1: 2](#)).

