7.3 PLANNED ANALYSES

During the Phase I Dose Escalation part, cohorts of patients treated with BI 836858 in combination with decitabine will be evaluated continuously based on the totality of the safety data available in order to determine the MTD (or RExP1D if applicable).

After determination of the RP2D in the Phase I Extension part and optional additional Dose Escalation cohort(s), a safety analysis report or lean interim CTR will be written to justify the RP2D prior to the initiation of Phase II.

The primary analysis of all primary, secondary and further efficacy endpoints will be conducted at the end of the whole trial ([Section 6.2.3.3](#)).

Efficacy analysis in Phase II will be based on the randomised set. This patient set includes all randomised patients, regardless of whether or not they have received treatment. For Phase I, efficacy endpoints will be summarized descriptively based on the treated set. No comparison will be done between cohorts.

The treated set includes all patients who have received at least one dose of study medication (BI 836858 and/or decitabine).

Safety analysis will be based on the treated set and will be summarized separately for patients treated in the Phase I and Phase II part of the trial.

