3. INTRODUCTION

As per ICH E9([1](#)), the purpose of this document is to provide a more technical and detailed elaboration of the principal features of the analysis described in the protocol, and to include detailed procedures for executing the statistical analysis of the primary and secondary variables and other data.

This TSAP assumes familiarity with the Clinical Trial Protocol (CTP), including Protocol Amendments. In particular, the TSAP is based on the planned analysis specification as written in CTP section 7 "Statistical Methods and Determination of Sample Size". Therefore, TSAP readers may consult the CTP for more background information on the study, e.g., on study objectives, study design and population, treatments, definition of measurements and variables, planning of sample size, randomisation. This TSAP follows the Boehringer Ingelheim (BI) internal reference ([2](#)).

This TSAP is based on the Project SAP wherever possible. Wordings like "randomisation (first administration of study treatment in non-randomised trials)" should therefore be interpreted as applicable.

Furthermore, in this combination trial the term investigational medicinal product is used for BI 836858 while combination drug denotes the backbone chemotherapy decitabine. The term trial medication is used for any of the two trial drugs.

SAS Version 9.4 or later version will be used for all analyses.

Due to company decision to stop this project, there is no Phase II subject enrollment so that Phase II analyses stated in CTP will be omitted.

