7. PLANNED ANALYSIS

The labelling and display format of statistical parameters will follow the guideline “Reporting of Clinical Trials and Project Summaries” [\(7\)](#).

For End-Of-Text (EoT) tables, the set of summary statistics is: N / Mean / Standard deviation (SD) / Min / Median / Max.

For tables that are provided for endpoints with some extreme data, median, quartiles and percentiles will be preferred to mean, standard deviation, minimum and maximum.

In general, means, medians, SD and percentiles will be presented to one more decimal place than the raw data. Minima and maxima will be presented to the same number of decimal places as the raw data.

Tabulations of frequencies for categorical data will include all possible categories (even if with no count and also the missing category if there is missing data) and will display the number of observations in a category as well as the percentage (%) relative to the number of subjects in the respective treatment group (unless otherwise specified, all subjects in the respective subject set whether they have non-missing values or not). Percentages will be rounded to one decimal place. The category missing will be displayed only if there are actually missing values.

If a table presents only categorical data, “N (%)” will be displayed in the column header only.

Abbreviations (e.g., Wors.) or acronyms (e.g., PD) will not be displayed in tables and Subject Data Listings (SDLs) without any explanation. They will be either spelled out or explained in footnotes.

If applicable, conversion from days to weeks, months and years will be as follows:

- Weeks = days \div 7
- Months = $12 \times$ days \div 365.25
- Years = days \div 365.25

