7.8 SAFETY ANALYSIS

All safety analyses will be performed on the treated set.

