An overall summary of adverse events will be presented. This will include the number of subjects with AEs by worst CTCAE grade. The frequency of subjects with adverse events will be summarized by treatment, primary system organ class and preferred term. The system organ classes will be sorted by default alphabetically; preferred terms will be sorted by frequency (within system organ class).

AEs leading to dose reduction, AEs leading to overall permanent discontinuation, DLTs and Adverse events of special interest (AESIs) including Infusion Related Reactions (IRRs) will be tabulated.

Infusion related reactions (IRRs):

IRRs will be the object of special attention.

Subjects with any IRR will be tabulated by treatment and worst CTCAE grade. In addition, the number of infusions and the number of IRRs will be displayed by treatment.

The duration of IRR [h] and the time since start of the respective infusion [min] together with IRR related symptoms will be tabulated by infusion number and overall.

- Duration of IRR [h] = (End time of IRR - Start time of IRR) [seconds] / 3600
- Time since start of the respective infusion [min] = (Start time of IRR - Start time of infusion) [seconds] / 60

The relationship between the occurrence of IRRs and infusion rate as well as the administration of premedication will be examined.

For IRR summary, time since administration of treatment, duration of IRR, and related symptoms will be summarized descriptively by infusion timepoints.

User-defined AE categories (UDAEC)

User-defined AE categories (UDAEC) are defined in Table 7.8.1:1. For UDAECs which contain sub-searches and/or two sensitivity levels (broad and narrow) all possibilities will be displayed on the UDAEC level in tables. For example for UDAEC “Infusion related infections” the tables will include the UDAEC “Infusion related reactions broad” and “Infusion related reactions narrow”. Similarly for UDAEC “Bleeding”, it will include “Bleeding - SMQ Haemorrhage”, “Bleeding - SMQ Haemorrhage laboratory terms broad”, “Bleeding - SMQ Haemorrhage laboratory terms narrow”, “Bleeding - SMQ Haemorrhage terms (excl. laboratory terms) narrow”.

Table 7.8.1:1 Definition of user-defined AE categories

Special Search Category	Definition	Sensitivity
Infusion related reactions (hypersensitivity)	SMQ 20000021 + infusion related reaction PT 10051792	Narrow (Algorithm)
Bleeding	SMQ Haemorrhage 20000038	Narrow & broad
	SMQ Haemorrhage terms (excl. laboratory terms) 20000039	Narrow

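### If any Phase I patients received only decitabine, the treated-set denominator understates the subject-level IRR percentages by dose cohort

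*SAP*

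**What the plan says.** - **Who is in the set.** SAP 6.3 on the treated set: "This subject set includes all subjects who were documented to have received at least one dose of trial medication". SAP 3 settles what that covers: "The term trial medication is used for any of the two trial drugs". Protocol 7.3 agrees, naming either drug or both.
- **Where the set is used.** SAP 7.8: "All safety analyses will be performed on the treated set". Protocol 7.3 and 7.3.4 also base safety on all treated patients.
- **How percentages are formed.** SAP 7 shows "the percentage (%) relative to the number of subjects in the respective treatment group" and, unless a table specifies otherwise, counts every subject of the set. SAP 6.1 fixes the groups: "subjects will be analysed by the dose cohort initially assigned in the first treatment course".
- **How a patient can miss BI 836858.** Decitabine starts on Day 1 and BI 836858 not before Day 8 (Protocol 4.1.3). Protocol 3.3.4.1 withdraws a Phase I patient who is not eligible for BI 836858 on Day 8, or Day 9 at the latest. For a high white cell count, footnote a of Table 4.1.3.1: 2 says "treatment with BI 836858 will not be initiated and the patient will be withdrawn from the trial treatment and replaced within the corresponding cohort". Footnote a of Table 4.1.3.2: 1 has the same rule for the extension cohorts.
- **What is tabulated.** SAP 7.8.1: "Subjects with any IRR will be tabulated by treatment and worst CTCAE grade". The same section counts infusions and IRRs by treatment, and summarises IRR duration, timing and symptoms by infusion number. IRRs of grade 3 or higher are also adverse events of special interest.

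The visible SAP text defines no BI 836858-exposed set and names no other denominator for these tables.

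**The concern.** A patient withdrawn before the first BI 836858 infusion has had about a week of decitabine and so belongs to the treated set, under an assigned BI 836858 dose. Protocol 5.3.1 ties IRRs to the administration of BI 836858, so this patient can enter the denominator of the IRR percentage but never the numerator. The bias runs in one direction, and it can differ between dose cohorts if the number never infused differs.

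The SAP singles out IRRs for special attention, and Protocol 2.3 reports them as the most frequent drug-related event in the first-in-human trial. SAP 7.4 leaves replaced patients out of the MTD determination but makes no matching provision for infusion-linked safety rates.

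The potential-TLS algorithm in SAP 7.8.1 has the same structure. Its laboratory criterion counts only values on the day of a BI 836858 infusion or the six days after it, so a never-infused patient cannot qualify. The SAP names no percentage table for this algorithm, so the point applies there only if an incidence is reported.

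**Working it through.** **Inputs**

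- IRR rate among infused patients: Protocol 2.3 gives 7 of 20, and 7/20 = 0.35 reproduces its 35%. It comes from another trial (relapsed or refractory AML, 10 and 20 mg), so here it is an illustrative assumption.
- Treated patients: the Protocol Synopsis gives 16 in escalation and 33 in extension, so N = 16 + 33 = 49. Taking this as the size of the treated set is an assumption.
- Patients never infused, k: not given, so shown over a range.

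**Formula**

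With x patients having an IRR, the rate among infused patients is p = x/(N − k). The tabulated rate is x/N = p × (N − k)/N. The relative understatement is k/N.

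**All Phase I patients, N = 49, p = 35%**

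| k | Tabulated rate | Relative understatement |
|---|---|---|
| 0 | 35.0% | 0% |
| 1 | 0.35 × 48/49 = 34.3% | 2.0% |
| 3 | 0.35 × 46/49 = 32.9% | 6.1% |
| 5 | 0.35 × 44/49 = 31.4% | 10.2% |
| 8 | 0.35 × 41/49 = 29.3% | 16.3% |

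**An extension cohort of 15 infused patients plus replaced patients, p = 35%**

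- One replaced: 0.35 × 15/16 = 32.8%.
- Two replaced: 0.35 × 15/17 = 30.9%.
- Three replaced: 0.35 × 15/18 = 29.2%.

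**An escalation cohort of 3 infused patients, one with an IRR**

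Whole patients have to be counted here, because 35% of 3 is not attainable.

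- None replaced: 1/3 = 33.3%.
- One replaced: 1/4 = 25.0%.
- Two replaced: 1/5 = 20.0%.

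**What does not move**

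- The MTD, because SAP 7.4 excludes replaced patients.
- The counts of infusions and of IRRs, and the summaries by infusion number, because a never-infused patient contributes nothing to them.

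**The case against.** The strongest reply is that the effect may be nil and is in any case small. No passage says that a patient went uninfused. The protocol also works against it: the decitabine lead-in is meant to lower the white cell count before Day 8, and hydroxyurea is allowed in Cycle 1. With k = 3, 16/46 = 34.8% (exact 95% CI 21 to 50%) becomes 16/49 = 32.7% (20 to 48%). In the small cohort, 1/3 (1 to 91%) becomes 1/4 (1 to 81%). Both shifts lie well inside sampling error. Safety is descriptive, Phase II is cancelled, and one treated population for a combination regimen is conventional. Listings of treated subjects, and of actual treatment at the onset of each event, also help a reader.

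Most of this stands as a limit on size. It does not remove the point: infusion counts and listings do not correct the subject-level or worst-grade percentages. Part of the SAP is not visible (Section 6.4, for instance), so an exposed set might be defined there. SAP 7.8 would still assign all safety analyses to the treated set.

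A reader might infer more than the documents support:

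- **That the rates are diluted in fact.** This needs k above zero, which is not shown.
- **That TLS rates in general are understated.** TLS reported as an adverse event can occur on decitabine alone, so decitabine-only patients are properly at risk. Only the infusion-anchored algorithm is affected.
- **That the hypersensitivity search category has the wrong denominator.** It could capture events unrelated to BI 836858.
- **That BI 836858 exposure summaries share the fault.** Their variables are in SAP 5.4.1, which is not visible, so this cannot be judged.

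**Conclusion.** The point holds conditionally. The written rules put decitabine-only patients in the denominator of the subject-level IRR tables. If there are any, each cohort's IRR percentage is understated by the fraction of that cohort never infused. Over all 49 patients the likely effect is small: about 0.7 percentage points for one such patient (35.0 − 34.3) and 3.6 for five (35.0 − 31.4). In a cohort of three infused patients a single replacement moves 33.3% to 25.0%. These figures rest on the assumed 35%, on 49 as the size of the treated set, and on an unknown k. No dose decision through the MTD is affected. This is a cheap improvement to safety reporting and does not undermine the trial's main conclusions.

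**What to change.** - Add to SAP 6.3 a flag or set for subjects with at least one BI 836858 infusion.
- Use it as the denominator for the subject-level IRR tables, including IRR of grade 3 or higher, and for any incidence reported from the infusion-anchored potential-TLS algorithm.
- State the number of decitabine-only patients in each dose cohort.
- Keep the treated set for overall AE tables, TLS reported as an AE and all other safety outputs.
- Record the change in SAP 4, because it departs from the treated-set rule in Protocol 7.3 and 7.3.4.

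The cost is one flag derived from infusion data already collected. The small downside is that the IRR tables will carry a different N from the other safety tables, which a footnote can explain. If no patient went uninfused, the numbers do not change.
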